12.1.7. Adverse Event Assessment

At all visits and phone contacts, including an ET or Unscheduled Visit, site staff will ask nonleading questions regarding the participant's health status (Section 12.3.1) and document any new or changed AEs. Adverse events occurring during washout periods (i.e., between Visit 1 and Visit 2, and between Visit 2 and the Telephone Follow-up Visit) should be collected at the next participant contact.

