### 10.2. Adverse Events

Any detrimental change in the participant's condition after signing informed consent and up to completion of the follow-up period after the last administration of study drug (i.e., through Follow-up [Day 15]) will be considered an AE and must be recorded.

All AEs will be classified by system organ class (SOC) and preferred term (PT), according to the Medical Dictionary for Regulatory Activities (MedDRA) version 27.0. The severity of AEs will be classified by the site investigator using the National Cancer Institute's (NCI's) Common Toxicity Criteria for Adverse Events (CTCAE) version 5.0. Relationship of AEs to study therapy (not related, unlikely related, possibly related, probably related, definitely related) will be assessed by the site investigator, based on their opinion. For summaries of study drug related AEs, the categories of "possibly related", "probably related", and "definitely related" will be considered study drug related. If the relationship is missing, it will be counted as "related" in summaries.

Treatment-emergent AEs are defined as AEs occurring after the participant received at least one dose of atropine. Treatment-emergent AEs will be identified as those with an onset date on or after the first dose of study medication.

If the start date of an AE is incomplete or missing, it will be assumed to have occurred on or after the first dose of investigational product, except if an incomplete date (e.g., month and year) clearly indicates that the event started prior to treatment.

The following conventions will be used for imputing missing start dates.

- For start dates that are missing the day value with non-missing month and year:
  - If the start year is the same as the year of first dose date, then do the following:
    - If the start month is the same as the month of first dose date, the start date will be imputed as the date of first dose date.

- If the start month is not the same as the month of first dose date, then the start date will be imputed as the first day of the non-missing start month.
  - If the start year is not the same as the year of first dose date, then the start day will be imputed as the first day of the start month.
- For start dates that are missing the day and month values with non-missing year:
  - If the start year is the same as the year of first dose date, the start date will be imputed as the date of first dose date.

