  - If the start year is after the year of first dose date, the start month and start day will be imputed as January 1.
- Completely missing start dates will be imputed as the date of first dose date.

End dates will not be imputed.

If a participant experiences the same AE on multiple occasions, the event will be counted once for each occurrence when reporting the number of AEs. When reporting the number of participants experiencing the events, a participant will only be counted once if they experience at least one event within the particular SOC or PT. Percentages will be based on the number of participants in the safety population.

Additionally, when summarizing AEs by severity or relationship, the AE will be categorized according to the highest severity (or relationship) rating for that AE in that participant.

Each AE will be assigned to a route of administration based on the most recently received route of administration prior to the beginning of the adverse event. In order to standardize the follow-up time after each study route administration, summaries will include treatment-emergent AEs or serious AEs (SAEs) through 7 days after the last study route administration, inclusive of the study route administration day. In addition, treatment-emergent AEs and SAEs through study participation will be presented.

- An overall summary table of TEAEs throughout the study and through 7 days after last study drug dose will include:
  - Total number of TEAEs
  - Total number of TEAEs related to study drug
  - Total number of serious TEAEs
  - Total number of serious TEAEs related to study drug
  - Total number of severe (grade 3, 4, or 5) TEAEs
  - Total number of severe (grade 3, 4, or 5) TEAEs related to study drug
  - Total number of TEAEs leading to early termination of study drug

- Total number of TEAEs leading to early study withdrawal
- Total number of TEAEs leading to death
- TEAEs classified by MedDRA SOC and PT will be summarized for each route of administration and overall for all TEAEs throughout the study and through 7 days after last study drug dose, separately.
- TEAEs classified by MedDRA SOC, PT, and maximum severity will be summarized for each route of administration and overall for all TEAEs throughout the study and through 7 days after last study drug dose, separately.

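### SAP 10.2 anchors incomplete AE start dates to the first dose only, so most Period 2 AEs with such dates would be tabulated under the Period 1 route

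*SAP*

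**What the plan says.** SAP 10.2 (Adverse Events) gives these rules for incomplete AE start dates:

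- Day missing, month of onset equal to the month of the first dose: "If the start month is the same as the month of first dose date, the start date will be imputed as the date" of the first dose.
- Day missing, month different: "then the start date will be imputed as the first day of the non-missing start month".
- Day and month missing, year equal to that of the first dose: "If the start year is the same as the year of first dose date, the start date will be imputed as the date" of the first dose.
- Nothing known: "Completely missing start dates will be imputed as the date of first dose date".

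End dates are not imputed. The second dose, the period and the contact at which the AE was reported play no part.

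The section then sets the route from AE onset, in a sentence quoted here up to its last two words: "Each AE will be assigned to a route of administration based on the most recently received route of administration prior to the beginning of the". It makes no separate provision for imputed dates. SAP 10.1 and 10.2 present AE tables by route and overall, both for the whole study and for a window of 7 days after dosing.

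On treatment emergence, SAP 10.2 first repeats the definition in Protocol 12.3.2 (onset after at least one dose). It then applies it by date: "Treatment-emergent AEs will be identified as those with an onset date on or after the first dose of study medication".

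Protocol 12.1.7 has AEs asked about at every visit and call. AEs arising between visits "should be collected at the next participant contact".

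**The concern.** A first-dose anchor is harmless where a participant has one treatment. Here each participant changes route at Visit 2: SL to IM in sequence A, IM to SL in sequence B. An AE that began after Visit 2 but has an incomplete date is usually pulled back before Visit 2, and the route rule then credits it to the route given at Visit 1. This can happen even if the AE was absent at the Visit 2 pre-dose review and first reported at the follow-up call.

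The by-route tables are the planned AE comparison of SL with IM. Each misplaced AE leaves one column and enters the other, and with about 46 participants single events are visible in such tables.

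A smaller point concerns dosing days. An AE on Day 1 before dosing, for example at placement of the sampling catheter (Protocol 11), is treatment-emergent by date but not by the definition, and no route has yet been received.

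**Working it through.** The documents state no figure on this point, so there is none to reproduce. The check applies the SAP rules literally to calendar dates.

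**Inputs**
- Visit 2 is Visit 1 + 7 days, ±1 (Protocol Appendix 2). The base case uses 7.
- The follow-up call is Visit 2 + 7 days, -1/+7 (Appendix 2), so onset can be up to 14 days after Visit 2.
- First enrolment is April 2024 and last completion August 2024 (Protocol Synopsis). Visit 1 is taken on each of the 122 dates from 1 April to 31 July 2024. The last of these gives Visit 2 on 7 August and the latest call on 21 August.
- Assumption: visit dates and onset days are evenly spread.

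**Only the year known, or no date.** Both doses fall in 2024, so the imputed date is always Visit 1. The wrong-route share is 100%.

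**Only the day missing.** Three examples for sequence A:
- Visit 1 on 10 May, Visit 2 on 17 May, onset 19 May. The month matches Visit 1, so the date becomes 10 May and the route SL (wrong).
- Visit 1 on 28 May, Visit 2 on 4 June, onset 6 June. The date becomes 1 June, before Visit 2, so SL (wrong).
- Visit 1 on 22 May, Visit 2 on 29 May, onset 2 June. The date becomes 1 June, after Visit 2, so IM (right).

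The route is right only if a first of the month falls between Visit 2 and onset, inclusive. For onset k days after Visit 2, that holds for k + 1 Visit 2 dates per month boundary. Four boundaries are in range (1 May, 1 June, 1 July, 1 August), so:

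wrong out of 122 = 122 - 4(k + 1) = 118 - 4k

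| Onset after Visit 2 | Calculation | Wrong route |
|---|---|---|
| Day 0 | 118/122 | 97% |
| Day 6 | (118 - 24)/122 = 94/122 | 77% |
| Days 0 to 6 | (7×118 - 4×21)/854 = 742/854 | 87% |
| Days 0 to 14 | (15×118 - 4×105)/1830 = 1350/1830 | 74% |
| Day 14 | (118 - 56)/122 = 62/122 | 51% |

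**Sensitivity**
- If an imputed date equal to the Visit 2 date is credited to Period 1, the count is 122 - 4k. The shares become 100% (day 0), 770/854 = 90% (days 0 to 6), 1410/1830 = 77% (days 0 to 14) and 66/122 = 54% (day 14).
- With Visit 1 dates to 31 August, gaps of 6, 7 and 8 days and onsets after 31 August dropped, the shares are 426/438 = 97.3% (day 0), 2667/3003 = 88.8% (days 0 to 6), 4815/6255 = 77.0% (days 0 to 14) and 216/396 = 54.5% (day 14).

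**Direction.** In that wider enumeration, 0 of 3149 Period 1 AEs changed period. The error runs only from Period 2 to Period 1.

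**The 7-day tables.** In the base case every misassigned AE is dated 0 to 6 days after dose 1. It therefore also enters the 7-day by-route tables under the wrong route. With an 8-day gap the date can fall on day 7.

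**The case against.** The strongest reply is that the percentages describe a share of very few events. Participants stay in clinic for 8 hours after each dose (Protocol 7.1), AEs are asked about at each contact roughly a week apart, and entry is contemporaneous with monitor verification and investigator sign-off (Protocol 15.1). This stands: the documents give no count of incomplete dates, and it is probably small.

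The link is also inferred. The SAP assigns route from the beginning of the AE and does not say that this means the imputed date. It offers no other start date, however, so this is the natural reading.

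The consequence is limited too. The Protocol Synopsis names PK parameters only as the criteria for evaluation, and the AE tables are descriptive. Post-dose blood pressure and heart rate are summarised by dose received (SAP 10.5.1), independently of AE dates.

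A reader might infer more in four ways, none of which the documents support:
- **That 87% holds throughout follow-up.** The share falls with time since dose 2. In the first-of-month branch, the imputed date precedes Visit 2 in 168/280 = 60% of cases over days 0 to 6, but in only 360/840 = 43% over days 0 to 14.
- **That serious events are a likely casualty.** Serious AEs are reported within 1 business day (Protocol 12.3.2), and related Grade 3 or higher AEs trigger review (Protocol 7.4). These are the AEs least likely to lack a date at lock.
- **That one route is favoured.** Sequence A moves IM events to SL and sequence B moves SL events to IM. Under 1:1 allocation this tends to blur the comparison, although the moves need not cancel.
- **That pre-dose Day 1 AEs will certainly be counted as treatment-emergent.** Two adjacent SAP sentences disagree, and the text does not settle which governs.

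**Conclusion.** The point holds as a defect in the stated rule with a limited effect. More than half of Period 2 AEs with incomplete dates would be credited to the Period 1 route in every scenario tested. This rests on the imputed date feeding the route rule, on the planned 2024 calendar and on evenly spread dates. How far the tables would change cannot be sized, because the number of incomplete dates is unknown. The primary PK analysis and the treatment-emergent status of these Period 2 AEs are unaffected. The change is worth making before lock because it is cheap and the present rule ignores the period altogether. The treatment-emergence wording is a secondary ambiguity to tidy at the same time.

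**What to change.** In SAP 10.2:

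1. Where an incomplete start date is compatible with either period, impute it to the most recent dose before the contact at which the AE was first recorded. Keep the first-dose anchor only for AEs first recorded before dose 2.
2. Use any AE end date before Visit 2 to place the AE in Period 1.
3. If the contact of first report is not captured and the period cannot be determined, show the AE as route undetermined or in a sensitivity table.
4. State that route is assigned from the date so imputed.
5. For dosing-day AEs, align the definition of treatment emergence with its date rule. Use onset time against dose time (dose time is already listed under SAP 8.3), or the pre-dose versus post-dose assessment, where captured.

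The cost is a few lines of SAP text and programming, plus a check of the eCRF. Appendix 2 shows when AEs are asked about. The documents do not show that the AE form stores the visit of first report or the onset time, so steps 1 and 5 depend on that check and step 3 is the fallback for step 1.

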8.2.2. Randomization of Additional Study Participants

In order to achieve the target number of evaluable participants within the per protocol analysis population, additional participants will be randomized to account for any participants who are randomized but do not receive the first dose of study drug.

If a participant is withdrawn from the clinical study after receipt of the first dose of study drug at Visit 1 and prior to completing the second dose of study drug at Visit 2, the participant will be removed from the per protocol population. Additional participants may be randomized to achieve the target number of evaluable participants within the per protocol analysis population.

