### 5.4. Safety Population

The safety population will include all participants who receive at least 1 study drug dose. Each participant's data will be analyzed according to the corresponding route of administration for the applicable period. The safety population will be used for all safety displays.

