## 7. STUDY PARTICIPANTS

### 7.1. Disposition of Participants

The disposition of all consented participants will be tabulated and listed. The numbers and percentages of participants consented, randomized, and terminating early, including reasons for early termination, will be presented. Percentages will be based on the number of participants at each level of summarization and within the specific study group, as applicable.

In addition, the reasons for ineligibility at screening/first study drug administration and ineligibility at the time of the second study drug administration will be listed separately.

Participants in each analysis population will be tabulated and listed for all randomized participants.

Visit completion will also be summarized for all randomized participants.

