### 8.3. Measures of Treatment Compliance

Study drug administration adherence for each route of administration will be summarized and listed. Counts and percentages of participants receiving dose 1 and dose 2, separately, will be reported in tables; the denominator will be the number of participants within each group as randomized. For participants who receive both doses of study drug, the counts and percentages of subjects receiving both doses of study drug according to the correct dosing sequence will be summarized. For participants terminating study drug administration early, the reasons for terminating study drug early will also be presented.

Details will be listed for each administration, including date and time of administration, route received, whether full dosage was received, why full dose not received, and location of intramuscular administration/time held for sublingual administration.

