## 10. SAFETY EVALUATION

### 10.1. Overview of Safety Analysis Methods

All safety analyses will be carried out using the safety population defined in Section 5.3 unless otherwise noted.

Summary tables will present adverse events (AEs) summarized by route of administration and overall.

Listings will be prepared for all safety measurements. Unless noted otherwise in a specific section, all listings will be sorted in order of participant identifier (ID) and time of assessment (e.g., visit, time, and/or event).

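### Does SAP 10.2 give the wrong denominator for adverse-event percentages by route?

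*SAP*

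**What the plan says.** SAP 10.1 requires adverse-event tables by route and overall. SAP 10.2 repeats this for each display: TEAEs by system organ class and preferred term "will be summarized for each route of administration and overall for all TEAEs throughout the study", with further tables by severity, relationship and seriousness. An event goes to the route most recently received before it began, which settles the numerator. For the denominator the section says only: "Percentages will be based on the number of participants in the safety population".

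SAP 5.4 defines that population in two steps. The first is membership: "The safety population will include all participants who receive at least 1 study drug dose". The second is handling: each participant's data are "analyzed according to the corresponding route of administration for the applicable period". Protocol 13.1.2.1.3 has the same handling rule.

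Protocol 8.2.2 provides for a participant "withdrawn from the clinical study after receipt of the first dose of study drug at Visit 1 and prior to completing the second dose". Such a person belongs to the safety population but has received one route only.

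Other sections define their own bases. Disposition in SAP 7.1: "Percentages will be based on the number of participants at each level of summarization and within the specific study group, as applicable". Compliance in SAP 8.3: "the denominator will be the number of participants within each group as randomized". SAP sections 2 and 16 place the table specifications and shells in separate documents, which are not available here.

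**The concern.** In a crossover study the by-route columns share most of their participants but not necessarily all. If the sentence in SAP 10.2 is applied without the rest of SAP 5.4, every column has the same N, namely everyone dosed at least once. A participant who received SL at Visit 1 and then withdrew would add one to the IM denominator with no chance of contributing an IM event. IM incidence would then be understated. If losses after dose 1 were unequal between sequences, the two routes would be understated by different amounts, and an SL-IM difference could be created or exaggerated.

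Two features make the omission noticeable. SAP 10.2 has an explicit by-route numerator rule but no matching denominator rule. And SAP 7.1 and 8.3 do specify group-level denominators for their own tables.

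At stake are the printed percentages in the by-route adverse-event tables.

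**Working it through.** **Reading the text.** The denominator sentence in SAP 10.2 takes its meaning from the definition in SAP 5.4.

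- Membership rule: at least one dose. Applied alone, it gives one N for all columns.
- Handling rule: data are analysed by the route given in the applicable period. A participant never given IM has no IM period and contributes nothing to an IM column.

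Taken together, the rules give the number dosed by that route for each route column and the whole safety population for the overall column. The single-N reading needs the second rule to be set aside.

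The contrast with SAP 7.1 and 8.3 shows little. The base in 8.3 is participants as randomized, which can include people never dosed. Neither section defines a route-exposed N that was then left out of 10.2.

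**The plan's own figure.** Protocol 13.2 plans about 46 randomized (23 per sequence) for 36 evaluable (18 per sequence) with 20% dropout.

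- 36 / (1 − 0.20) = 45, close to the stated 46.
- 46 × 0.80 = 36.8, consistent with about 36.
- Planned gap: 46 − 36 = 10, or 10/46 = 21.7%.

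**Size of the effect if the single N were used.** Assume all 46 receive dose 1. Let *a* be the number in Sequence A (SL first) who never receive IM, and *b* the number in Sequence B (IM first) who never receive SL. The documents give neither, so the values below are assumptions.

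- N dosed SL = 46 − b; N dosed IM = 46 − a.
- Printed percentage = true percentage × (N dosed by that route) / 46.

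| a, b | N SL | N IM | SL factor | IM factor | An assumed 50% prints as (SL / IM) |
|---|---|---|---|---|---|
| 0, 0 | 46 | 46 | 1.000 | 1.000 | 50.0% / 50.0% |
| 1, 1 | 45 | 45 | 0.978 | 0.978 | 48.9% / 48.9% |
| 2, 2 | 44 | 44 | 0.957 | 0.957 | 47.8% / 47.8% |
| 5, 5 | 41 | 41 | 0.891 | 0.891 | 44.6% / 44.6% |
| 10, 0 | 46 | 36 | 1.000 | 0.783 | 50.0% / 39.1% |

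The last two rows put the whole planned gap of 10 after dose 1. They are stress cases and not forecasts. The planned gap is a loss from the per protocol population, so it can include people never dosed and people dosed by both routes but excluded for deviations. Nor is 10 a ceiling, because Protocol 8.2.2 and 13.2 allow extra participants to be randomized. Planned loss is balanced (23 to 18 in each sequence), and balanced loss gives equal factors and no spurious difference between routes.

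**Can a reader recover the rate?** Yes. SAP section 4 prints n with the percentage, and SAP 8.3 summarizes dosing by route. For example, 10 participants with an event print as 10/46 = 21.7% on the single N. Dividing by 45 dosed gives 22.2%. The overall summary in SAP 10.2 lists total numbers of events, which need no participant denominator.

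**The case for a change.** The best argument for a change is that two programmers could follow SAP 10.2 in good faith and print different numbers. The same denominator sentence appears in SAP 7.3 for medications, where summaries are overall and by class and the whole safety population is the right base. It could have been carried into 10.2 without thought for route columns. The handling rule in SAP 5.4 assigns data to a route and does not state an N.

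Unequal loss is also possible. Protocol 7.4.1 allows dosing to stop after an adverse event. If one route were less well tolerated, more people who started on it might never receive the other. The single N would then dilute the better-tolerated route and widen the apparent gap. The SAP has to be final before database lock, and one sentence would remove the doubt.

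Some of this stands: the SAP does not state the by-route N, and the shells cannot be checked here. But the direction of any unequal loss is conjecture, since the documents give no loss rate by route. The harm needs three things together: the less natural reading, shells that adopt it, and a material number of single-route participants. A clarifying sentence would do no harm, but the analysis the plan supports is the same without it.

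**Conclusion.** No change to the plan follows. This is an unstated convention that analysts fill sensibly: route columns use those dosed by that route, and the overall column uses everyone dosed. SAP 5.4 points to that reading.

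If the single N were used instead, the understatement would be zero when all dosed participants receive both routes. It would be about 2% in relative terms with one single-route participant per sequence out of 46 (factor 0.978). It would be about 11% if five per sequence were lost after dose 1 (factor 0.891). These sizes assume 46 dosed and loss counts that the documents do not give. A difference between routes arises only from unequal loss. The synopsis limits the evaluation criteria to pharmacokinetic parameters, the adverse-event tables are descriptive, and the bioequivalence decision on AUC to infinity and AUC to the last quantifiable point does not use them.

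Two section numbers are clerical slips and add no weight. SAP 10.1 reads "All safety analyses will be carried out using the safety population defined in Section 5.3 unless otherwise noted", but the safety population is Section 5.4. SAP 8.1 cites Section 5.5 for the per protocol population, which is Section 5.6. Both name the population correctly, so the intent is clear.
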